### **12.18 Urine Cotinine**

Urine samples will be collected and tested using an on-site one-step rapid nicotine test stick to determine qualitative detection of cotinine levels at 200 ng/mL cut-off concentration.

### **12.19 EtG Urine Alcohol Test**

Urine samples will be collected and tested using an on-site one-step rapid ethyl glucuronide (EtG) test stick to determine qualitative detection of alcohol levels at 500 ng/mL cut-off concentration and be used to evaluate the abstinence from the consumption of alcohol.

## **12.20 Urine BE Testing**

Urine samples will be collected and sent to a central laboratory (Laboratory Corporation of America, Research Triangle Park, NC) to be analyzed for BE and creatinine using validated liquid chromatography-tandem mass spectrometry methods for analysis. The details of sample collection, labeling, storage, and shipment will be provided in a Study Operations Manual.

## **12.21 Blood Collections for Medication Adherence**

As specified in **Table 3, Schedule of Events**, blood samples will be collected to determine the plasma concentrations of both acetazolamide (Study Day 8) and lorcaserin (Study Weeks 3 and 7) as a medication adherence marker. Each blood sample will be collected into a sodium heparin-containing Vacutainer® tube, and plasma will be separated according to standard procedures. Plasma concentrations of ACZM and lorcaserin will be determined at a central bioanalytical lab (XenoBiotic Laboratories, Inc., Plainsboro, NJ) using a validated liquid chromatography-tandem mass spectrometry method. The details of sample collection, labeling, storage, and shipment will be provided in a Study Operations Manual.

## **12.22 Cognitive Behavioral Therapy (CBT)**

Attendance at the clinic for assessments and the behavioral counseling session will be recorded on an eCRF including the length of the session. The Behavioral Counseling eCRF will also record any additional behavioral methods the subject may have used on their own, *e.g.*, NA, AA, hypnosis, etc.

## **12.23 Alcohol Intervention: Quit to Quit**

A computer-based alcohol intervention will be viewed by all subjects on Study Day 1 and will be continued on an optional basis at the discretion of each subject. The alcohol intervention, “Quit to Quit”, will encourage abstinence from alcohol but it will be up to each subject to decide whether or not this will be one of their goals during the trial. Each subject’s decision (yes or no) to continue viewing the alcohol intervention modules will serve as one of the stratification factors for randomization. The subject’s case report forms will contain a record of all alcohol intervention modules viewed.

## **12.24 AiView Adherence Monitoring**

Beginning on Study Day 8, subjects will participate in a medication adherence monitoring procedure, with associated opportunities to earn rewards that are contingent upon appropriate performance of tasks using a site-provided cell phone loaded with Health Insurance Portability and Accountability Act (HIPAA)-compliant AiView software (AiCure Technologies, New York, NY). AiView uses facial recognition and motion-sensing technology to confirm the ingestion of a study medication and transfers the resulting data (encrypted and blurred) to a secure central server in real time. The software will also be configured to remind patients of upcoming scheduled doses and record the previous day’s cocaine and alcohol use.

## **12.25 Concomitant Medications**

All medications taken by the subject within the 30 days prior to screening and during the screening period, up to and including the day of randomization, will be recorded. The reported medications will be reviewed and approved by the SI/study physician for possible interactions

with study drugs or an indication of a serious chronic or acute medical condition that would exclude the candidate from participation.

All medications taken by the subject during the Treatment Phase of the study through the Week 16 Follow-Up Visit will be recorded. Any medications taken during this time must be pre-approved by the SI/study physician whenever possible to avoid interactions with study drug.

NOTE: In general, participants who require any concomitant medications at the time of screening must have a stable medical condition and stable dosages for the 3 months prior to enrollment in the study. Subjects will be cautioned not to take concomitant medications, whether prescription, over-the-counter, herbal supplements, or health store products without first consulting with the SI or his/her designee. The NIDA Medical Monitor should be contacted if there are any questions.

### **12.25.1 Concomitant Medications Always Excluded**

In general, concomitant medications that have been associated with serotonin syndrome and drugs that are metabolized by CYP 2D6 are not permitted under this protocol. The list below contains medications that are specifically not allowed at any time during the course of study participation. In addition, section 12.23.2 delineates a list of concomitant medications with limitations of use. Again, if in doubt, consult a physician assigned to the study or the NIDA Medical monitor.

Including but not limited to:

- Antipsychotic Medications: haloperidol, thioridazine, aripiprazole, etc.
- All opioids: tramadol, oxycodone, hydrocodone, codeine, morphine, methadone, buprenorphine, etc.
- All beta-blockers: propranolol, metoprolol, etc.
- All Class I antiarrhythmic drug: flecainide, propafenone, mexiletine, etc.
- All monoamine oxidase inhibitors (MAOIs)
- Dexamphetamine, Lisdexamfetamine or Methamphetamine
- All tryptans, lithium, ondansetron, dolasetron, donepezil, metoclopramide, palonosetron, promethazine, safinamide, St. John's wort, tryptophan and any other dopaminergic or serotonergic drug that is not specifically listed as allowable in this protocol.
- Medications to treat erectile dysfunction (e.g. Viagra, Cialis, etc)

### **12.25.2 Allowable Concomitant Medications with Limitations**

Subjects will be allowed to receive **no more than** one medication, included in the list below, at any given time during the course of study participation.

- Non-MAOI antidepressants: amitriptyline, atomoxetine, bupropion, clomipramine, desipramine, desvenlafaxine, duloxetine, fluoxetine, fluvoxamine, imipramine, levomilnacipran, minanserin, mirtazapine, paroxetine, venlafaxine, vilazodone, and vortioxetine

- Dextromethorphan

### 12.26 Substance Use Report (SUR)

The SUR measures the subject's self-report of days of recent drug use. The use of cocaine, alcohol, nicotine, marijuana, methamphetamines, amphetamines, opiates, and benzodiazepines will be recorded on the SUR form. NOTE: Timeline Followback (TLFB) of cocaine and alcohol use will be obtained only for missing data beginning at Study Day 8 (data not captured by the AiView device).

### 12.27 Brief Substance Craving Scale (BSCS)

The BSCS is a self-administered assessment that asks the subject to rate his/her craving for cocaine. The BSCS used for this study is a modification of the State of Feelings and Cravings Questionnaire (Mezinskis et al., 2001). The composite BSCS severity score is a sum of three items: intensity, frequency, and length (each item ranges from 0 for no use to 4 for extreme use), ranging from 1 to 12. The higher the score, the more severe the cocaine craving is. However, members of study staff are not to offer interpretations of the questions.

### 12.28 Adverse Events

Adverse events will be assessed by medically trained study staff. If an adverse event requires medical attention, it will be reported to a study physician immediately. Adverse events will be assessed by asking the subject, "How have you been feeling since I saw you last?" **After current adverse events are assessed, the study physician must review with the subject and assess any adverse events unresolved from the previous visit.** After the adverse event assessment at each clinic visit, the type of adverse event, severity of each adverse event, and the relationship to the study drugs will be recorded on the Adverse Events eCRF, according to the procedures described in **Appendix I**. These categories are asking for the clinician's best judgment of the severity and relatedness of each adverse event.

As a precaution, all subjects will be closely monitored for treatment reports or signs of serotonin toxicity such as spontaneous clonus, inducible clonus with agitation or diaphoresis, ocular clonus with agitation or diaphoresis, tremor and hyperreflexia, hypertonia and hyperpyrexia with ocular or inducible clonus when adverse events are assessed during each weekly visit. The Hunter Serotonin Syndrome diagnostic criteria are noted in **Appendix I**.

**NOTE: All follow-up Week 16 AEs will be recorded and followed to resolution, only if they are serious, or if the study physician assesses them to be clinically significant.**

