### 13.10 Adverse Events Reporting

In accordance with FDA reporting requirements, all AEs occurring during the course of the clinical trial will be collected, documented, and reported by the SI or sub-investigator according to the specific instructions detailed in this section of the protocol and **Appendix I**. The occurrence of AEs will be assessed at each study visit beginning on the day the Informed Consent is signed through the Follow-up Visit at Week 16.

An AE is defined as any reaction, side effect, or untoward event that occurs during the course of the clinical trial, whether or not the event is considered investigational product-related or clinically significant. For this study, AEs will include events reported by the subject, as well as

clinically significant abnormal findings on physical examination or laboratory evaluation. A new illness, symptom, sign or clinically significant clinical laboratory abnormality or worsening of a pre-existing condition or abnormality is considered an AE. Stable chronic conditions, such as arthritis, which are present prior to clinical trial entry and do not worsen are not considered AEs. All AEs must be recorded on the AE CRF. The AE CRF is also used to record follow-up information for unresolved events reported on previous visits.

Each week, a study physician must review all new AEs reported the previous week and any events that were reported as continuing. All AEs, including clinically significant abnormal findings on laboratory evaluations, regardless of severity, will be followed by SIs until satisfactory resolution.

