### ***Follow-Up of All Adverse Events/Serious Adverse Events***

All adverse medical events must be followed until they are resolved, or until all attempts to determine the resolution of the AE/SAE are exhausted. This may require an extended hospitalization period or a change in status from outpatient to inpatient. All treatments, outcomes and information regarding whether or not the subject was referred to their Primary Care Provider for additional follow-up must be recorded in the source document. All serious and unexpected adverse events occurring at any time (up to and including the Week 16 visit) must be reported. All follow-up Week 16 AEs will be recorded and followed to resolution, only if they are serious, or if the study physician assesses them to be clinically significant.

The SI is required to provide the Medical Monitor and the NIDA Project Manager with all relevant follow-up information necessary to facilitate a thorough understanding of the event and judgment regarding the relationship to the study drug.

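### Section 12.28 and Appendix I put a condition on Week 16 adverse events that Section 13.10 does not: the follow-up rules conflict and, on the most natural reading, so do the recording rules

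*Combined protocol and SAP*

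**What the plan says.** Section 12.28 first gives a general rule: "After the adverse event assessment at each clinic visit, the type of adverse event, severity of each adverse event, and the relationship" to study drug go onto the AE form. No visit is exempted. A note at the end of the section then says: "All follow-up Week 16 AEs will be recorded and followed to resolution, only if they are serious", or if the study physician judges them clinically significant.

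Section 13.10 sets the period for AE assessment at each study visit as "beginning on the day the Informed Consent is signed through the Follow-up Visit at Week 16". It defines an AE as an untoward event "whether or not the event is considered investigational product-related or clinically significant". On recording it says: "All AEs must be recorded on the AE CRF". On follow-up it says that all AEs, "regardless of severity, will be followed by SIs until satisfactory resolution".

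Appendix I, part G, opens its paragraph on follow-up with "All adverse medical events must be followed until they are resolved" (or until attempts to establish the outcome are exhausted). It closes the same paragraph with the Week 16 sentence from 12.28.

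Table 3 schedules an AE assessment at both Week 14 and Week 16. Section 14.4 summarizes the incidence and severity of treatment-emergent AEs by treatment group.

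**The concern.** Week 16 is the last safety visit and, according to Section 7, falls more than two weeks after the last dose. For a subject who completes treatment, it is the only scheduled visit that can pick up events starting after the Week 14 visit, including any that follow stopping the drug.

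If the note in 12.28 is applied as written, some events at that visit that meet the protocol's own AE definition do not reach the database. A site working from 13.10 would enter them. The by-arm AE data for the closing weeks could then be incomplete, and incomplete to different degrees at different sites. A reader of the safety tables could not tell which rule a site had used.

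**Working it through.** No sample size, power figure or rate is involved, so the check sets the texts side by side. Take one test event: reported by a subject at Week 16, not serious, and not judged clinically significant by the study physician.

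1. **Is it an AE?** Yes. The 13.10 definition does not depend on clinical significance. That section admits abnormal examination and laboratory findings only when they are clinically significant, so the recording question falls mainly on symptoms and illnesses that subjects report.

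2. **Is it recorded, and is it followed?** The note can be read in two ways. In reading A the condition governs both verbs. In reading B it governs only the following to resolution.

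| Source | Recorded? | Followed to resolution? |
|---|---|---|
| 13.10 | Yes | Yes |
| 12.28, body text | Yes | Not addressed for new events |
| Appendix I, opening of the follow-up paragraph | Not addressed | Yes, or until attempts are exhausted |
| Week 16 sentence (12.28 and Appendix I), reading A | No | No |
| Week 16 sentence (12.28 and Appendix I), reading B | Yes | No |

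3. **Result.** Under reading A, recording conflicts with 13.10 and with the body of 12.28. Under both readings, follow-up conflicts with 13.10 and with the opening of the Appendix I paragraph. Reading A is the more natural one, because the two verbs are joined and the condition comes after both.

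4. **Scope.** After the randomization visit (Week 2), a completer has AE assessments at Weeks 3 to 14, which is 14 − 3 + 1 = 12 visits, and at Week 16, which is 1 visit. The total is 12 + 1 = 13. The conflict touches 1 of 13, the visit covering roughly the last two weeks. This is a share of visits, not of events. The documents give no AE rate for this period, so the number of events affected cannot be calculated.

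5. **Where the events would be used.** Section 14.2 assesses treatment-emergent AEs after randomization in relation to lorcaserin or placebo and gives no end date. Section 14.4 gives none either. As written, Week 16 events may enter the by-arm summary.

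**The case against.** The strongest defence is that the sentence means what reading B says. It begins by saying that all Week 16 AEs will be recorded, and the comma allows the condition to attach to follow-up alone. In Appendix I it stands under a heading about follow-up, and the body of 12.28 records AEs at every visit. This reading is tenable, and under it there is no recording conflict. It does not remove the follow-up conflict, and a sentence open to two readings is itself a way for sites to diverge.

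A second defence is that a specific note overrides a general rule. Section 13.10 refers to Appendix I, which carries the note, and the mention of Week 16 in 13.10 is attached to assessment, while its recording sentence is general. This has some force. But Appendix I contains both follow-up rules, so the cross-reference does not settle which one applies. An exception on recording would also sit badly with a definition that expressly sets clinical significance aside.

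A reader might infer more than the documents support:

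- **That non-serious Week 16 events are never entered.** They are entered if the study physician judges them clinically significant.
- **That nearly all Week 16 AEs would be lost, because all but one AE in the human laboratory study (Section 3.4.4) were mild.** That was a 26-subject study with a 7-day regimen and cocaine infusions, so it says nothing about an off-drug visit at Week 16. Mild is a severity grade and not a judgment of clinical significance. Table 2 classifies neither seriousness nor clinical significance.
- **That all off-drug AE counts are affected.** Week 14 events, events at the weekly visits of subjects who stop drug but remain in follow-up, and events at the Early Termination visit are outside the note.

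**Conclusion.** The inconsistency is real and minor. The follow-up rules in 12.28, 13.10 and Appendix I conflict however the Week 16 sentence is read. The recording rules conflict on its most natural reading.

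The consequence is a possible undercount of non-serious Week 16 events not judged clinically significant, and uneven recording between sites. Serious and clinically significant events are captured under either rule. A bias between arms is not to be expected, because site staff are blinded and randomization is blocked within site, so any loss should fall similarly on both groups. The summaries affected are descriptive.

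Two things limit how far this can be taken. The amount of data affected cannot be derived from the documents. Any effect on the Section 14.4 tables also assumes that Week 16 events count as treatment-emergent, which the plan neither states nor rules out.

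**What to change.** In Section 12.28 and in Appendix I, part G, replace the Week 16 sentence with one that says all AEs elicited at the Week 16 visit are recorded on the AE form, as Section 13.10 requires. Deal with follow-up in a separate sentence, so that no condition on follow-up can be read as a condition on recording.

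Then reconcile the follow-up wording in 12.28, 13.10 and Appendix I so that the same rule appears in all three. Which follow-up rule to adopt is for the sponsor and the study physicians, and this point takes no position on it.

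The cost is a few sentences and a few more AE entries at the final visit. No visit or assessment is added, since Table 3 already schedules AE assessment at Week 16. The gain is complete and uniform recording at the last safety visit.

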## 13 REGULATORY AND REPORTING REQUIREMENTS

### 13.1 Good Clinical Practices

This study will be conducted in accordance with the most current version of the International Conference on Harmonisation Guide for Good Clinical Practices (GCP).

### 13.2 FDA Form 1572

The SI agrees to sign and submit a Statement of Investigator (FDA Form 1572) to the sponsor prior to initiating this study.

### **13.3 IRB Approval**

Prior to initiating the study, the SI will obtain written IRB approval to conduct the study. Should changes to the study protocol become necessary, the SI will submit protocol amendments in writing to the IRB for IRB approval prior to implementation. In addition, IRBs will approve all advertising materials used for subject recruitment and any educational materials given to the subject. Annual reports and progress reports will be submitted to the IRB annually or at a frequency requested by the IRB.

The SI will ensure that a duly constituted IRB at the study site that conforms to FDA regulations (21 CFR Part 56) will review the protocol and the volunteer informed consent form. The SI will follow IRB and FDA guidance regarding reporting of AEs. The SI will promptly report to the IRB all changes in research activity and all unanticipated problems involving risks to human subjects or others and will not make any changes in the protocol without IRB approval, except where necessary to eliminate immediate hazards to human subjects.

### **13.4 Informed Consent**

The investigator, sub-investigators, study physician, or designated staff at each site will explain all aspects of the study in lay language and answer all of the candidate's questions regarding the study. If the candidate desires to participate in the study, s/he will be asked to sign and Informed Consent. No study procedure will be performed prior to signing Informed Consent. Candidates who refuse to participate or participants who withdraw from the study will be regarded without prejudice. All study subjects will be given a copy of the signed Informed Consent(s).

### **13.5 Use of Protected Health Information**

At the time of informed consent, all potential candidates will be asked to sign a waiver authorizing the release and use of protected health information in this study. Clinical sites will employ a Protected Health Information Disclosure that details the health information that will be collected as part of this research and the agencies that may access that information during the study and after the study has been completed.

Health information gathered during this research study may be reviewed by representatives of NIDA, the Food & Drug Administration (FDA) and designated appointees for monitoring purposes. All data collected for this study will be sent to the VA CSP Coordinating Center (CSPCC) in [name] for processing and analyses. Case report form data will be transmitted electronically to a secure server owned and operated by Medidata Solutions, Inc. The Medidata server is compliant with the Federal Information Security Management Act of 2002 (FISMA). Retrieval of data stored on the server is restricted to data management personnel at the VA CSPCC. De-identified data from third parties, such as clinical laboratory values or toxicology results, will be provided to the VA CSPCC electronically through NIDA's LiveLink server. Following retrieval of data, a database will be constructed and maintained locally at the VA CSPCC and all data contained within will be stored according to the HIPAA Privacy Rule.

## **13.6 Drug Accountability**

Upon receipt, the SI/pharmacist is responsible for taking inventory of the study drug. A record of this inventory must be kept and usage must be documented. Any unused or expired study drug shall be returned to the VA CSPCRPCC by the sites, unless otherwise instructed.

## **13.7 Monitoring**

### **13.7.1 Data and Safety Monitoring Board**

Blinded safety data will be reviewed by the NIDA Data and Safety Monitoring Board that will convene on a quarterly basis during the conduct of this study, or earlier, if deemed necessary.

The DSMB will make a recommendation to the sponsor regarding whether to stop or continue the study. If the DSMB determines that the study should be stopped, all subjects will be immediately discontinued from receiving any investigational products and no new subjects will be consented or randomized.

In addition, NIDA has the right to discontinue the investigation at any time.

